13.2.3 Additional Secondary Objectives

1. The average percentage (%) change in the CD8+ TIL density from TURBT to RC in each of the two cohorts. Each individual patient's percent change will be defined as $[(\text{Cystectomy TIL Density}) - (\text{TURBT TIL Density})] / (\text{TURBT TIL Density})$.
2. Proportion of patients in each cohort who do not get a radical cystectomy specifically and directly related to treatment related AEs within 6 weeks of the last dose of neoadjuvant treatment.
3. Proportion of patients with pathologic complete (pT0N0) and partial (<pT2N0) response in the two cohorts.
4. Proportion of patients who are alive and free of disease in each cohort at 2 years from registration.

13.2.3.1 Analytic Plan for Additional Secondary Objectives

1. The mean percent change of CD8+ TIL density from pre-treatment (TURBT) to post-treatment (radical cystectomy) samples in all 12 patients in Cohort 1 and all 24 patients in Cohort 2 will be calculated

and compared between the two cohorts using a Wilcoxon rank sum test.

2. The proportion of patients in each treatment cohort who do not get radical cystectomy specifically and directly related to treatment related AEs within 6 weeks of the completion of neoadjuvant treatment, will be reported along with exact binomial 90% confidence intervals for each cohort and compared between the two cohorts using Fisher's exact test.
3. The proportion of patients in each treatment cohort with pathologic complete response (CR) and pathologic partial response (PR) will be reported along with exact binomial 90% confidence intervals for each cohort.
4. Recurrence-free survival (defined as patients who are alive and without evidence of disease recurrence) from the time of registration will be estimated using Kaplan-Meier method for each treatment cohort and compared between the two cohorts using a log-rank test. One-year and two-year disease-free survival estimates and confidence intervals will be provided for each cohort.

13.2.4 Exploratory Objectives

1. The relationship between the expression of baseline IHC markers of interest (e.g. PD-1, PD-L1, PD-L2, NKG2D, KIR2DL1/2/3), and change in expression, for pathologic partial and complete tumor response (defined by cystectomy pathologic staging <pT2N0 and pT0N0, respectively), in patients treated with nivolumab and combination of nivolumab/lirilumab. To also compare the association of study cohort and pathologic response stratified by levels of expression of these biomarkers of interest.
2. The relationship between peripheral blood mononuclear cell (PBMC) T-cell subset status (%CD4+ T-cells, %CD8+ T-cells, %T_{reg} T-cells, %Myeloid Derived Suppressor Cells, %Natural Killer cells, etc.) and change in status, as assessed by flow cytometry analysis, for pathologic partial and complete tumor response (defined by cystectomy pathologic staging < pT2N0 and pT0N0, respectively), in patients treated with nivolumab and combination of nivolumab/lirilumab.
3. To compare the CD8+ TIL density at radical cystectomy between the patients treated with nivolumab and combination of nivolumab/lirilumab.
4. The prognostic and predictive relationship between pre- and post- treatment TIL and NK-cell level and activation and pathologic partial and complete response (defined by cystectomy pathologic staging <pT2N0 and pT0N0, respectively) as well as two-year RFS, in patients treated with nivolumab and combination of nivolumab/lirilumab.
5. To assess impact of prior BCG exposure on rates of pathologic partial and complete response (defined by cystectomy pathologic staging <pT2N0 and pT0N0, respectively) as well as two-year RFS, in patients treated with nivolumab and combination of nivolumab/lirilumab.
6. To assess the prognostic and predictive relationship of tumor mutational load, neo-epitope burden, intrinsic molecular subtypes (basal vs. luminal), and T-cell clonality with pathologic partial and complete response (defined by cystectomy pathologic staging <pT2N0 and pT0N0, respectively) as well as two-year RFS, in patients treated with nivolumab and combination of nivolumab/lirilumab

7. To assess the prognostic and predictive relationship of pre- and post-treatment T-cell subsets, CD4+/CD8+ and CD4+/FOXP3+ ratios and plasma cytokine multiplex panels with pathologic partial and complete response (defined by cystectomy pathologic staging <pT2N0 and pT0N0, respectively) as well as two-year RFS, in patients treated with nivolumab and combination of nivolumab/lirilumab.
8. To assess the prognostic and predictive relationship between pre- and post-neoadjuvant treatment levels in plasma cytokine biomarkers of interest (e.g. IFN- α , TGF- β , IL-10, IL-4, IL-5, IL-13, IFN- γ , etc.) and pathologic partial and complete response (defined by cystectomy pathologic staging <pT2N0 and pT0N0, respectively) as well as two-year RFS, in patients treated with nivolumab and combination of nivolumab/lirilumab.
9. To assess prognostic and predictive associations between baseline tumor and/or tumor infiltrating lymphocyte tissue and ctDNA genomic alterations, gene expression, and methylation signatures for pathologic partial and complete response (defined by cystectomy pathologic staging <pT2N0 and pT0N0, respectively) as well as two-year RFS, in patients treated with nivolumab and combination of nivolumab/lirilumab.
10. To assess prognostic and predictive value of serum circulating antibody profiles on pathologic partial and complete response (defined by cystectomy pathologic staging <pT2N0 and pT0N0, respectively) as well as two-year RFS, in patients treated with nivolumab and combination of nivolumab/lirilumab
11. To assess CD8+ TIL density by central pathology review using image analysis in TURBT and radical cystectomy in each arm.

13.2.4.1 Analytic Plan for Exploratory Objectives

As a general strategy, marker levels in responders vs. non-responders will be compared by a t-test or Wilcoxon rank sum test as appropriate. In addition to evaluating expression on a continuous scale we will explore quantile values for each marker as potential thresholds to discretize the marker levels. The two-year RFS will then be compared between marker groups with a Fisher's exact test as well as via time-to-event analyses using standard methods for survival analysis. Changes in biomarker levels will be computed and compared between groups using a Wilcoxon rank sum test. Analyses of the predictive ability of markers will be accomplished via standard tests of treatment-by-marker interaction using the appropriate model for the endpoint of interest (logistic regression or proportional hazards regression). Pearson's correlation and the Wilcoxon signed rank test will be used to characterize the relationship between CD8+ TIL densities produced by various methods of assessment. The study is not powered for these analyses, however, so conclusions regarding the predictive ability of any given marker will be limited.

14. Laboratory and Pathology Correlative Studies

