2.3 Exploratory Objectives

- To assess the prognostic and predictive value of the expression of baseline immunohistochemistry (IHC) markers of interest (e.g. PD-1, PD-L1, PD-L2, NKG2D, KIR2DL1/2/3), and change in expression, for pathologic partial and complete tumor response (defined by cystectomy pathologic staging <pT2N0 and pT0N0, respectively), in patients treated with nivolumab and combination of nivolumab/lirilumab.
- To assess the prognostic and predictive value of peripheral blood mononuclear cell (PBMC) T-cell subset status (%CD4+ T-cells, %CD8+ T-cells, %T_{reg} T-cells, %Myeloid Derived Suppressor Cells, %Natural Killer cells, etc.) and change in status, as assessed by flow cytometry analysis, for pathologic partial and complete tumor response (defined by cystectomy pathologic staging <pT2N0 and pT0N0, respectively), in patients treated with nivolumab and combination of nivolumab/lirilumab.
- To compare CD8+ TIL density in post-treatment RC tissues in patients treated with nivolumab and combination of nivolumab/lirilumab.
- To assess the prognostic and predictive relationship between pre- and post- treatment TIL and NK-cell level and activation and pathologic partial and complete response (defined by cystectomy pathologic staging <pT2N0 and pT0N0, respectively) as well as two-year RFS, in patients treated with nivolumab and combination of nivolumab/lirilumab.
- To assess impact of prior BCG exposure on rates of pathologic partial and complete response (defined by cystectomy pathologic staging <pT2N0 and pT0N0, respectively) as well as two-year RFS, in patients treated with nivolumab and combination of nivolumab/lirilumab.

- To assess the prognostic and predictive relationship of tumor mutational load, neo-epitope burden, intrinsic molecular subtypes (basal vs. luminal), and T-cell clonality with pathologic partial and complete response (defined by cystectomy pathologic staging <pT2N0 and pT0N0, respectively) as well as two-year RFS, in patients treated with nivolumab and combination of nivolumab/lirilumab.
- To assess the prognostic and predictive relationship of pre- and post-treatment peripheral blood T-cell subsets, CD4+/CD8+ and CD4+/FOXP3+ ratios and plasma cytokine multiplex panels with pathologic partial and complete response (defined by cystectomy pathologic staging <pT2N0 and pT0N0, respectively) as well as two-year RFS, in patients treated with nivolumab and combination of nivolumab/lirilumab.

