14.2.5 Cytokine Analysis

The pharmacodynamics functional effects of nivolumab and/or lirilumab will be analyzed by assessment of pre- and post-treatment plasma cytokine markers of interest (e.g. IFN- α , TGF- β , IL-10, IL-4, IL-5, IL-13, IFN- γ , etc.). The exact list of cytokines analyzed will be selected based on assay methodology optimization and validation testing. It is expected that a panel of a few markers will be analyzed to distinguish between major immune effector pathways. Additional exploratory analysis of the relationship between circulating free tumor DNA/RNA, micro-RNA, and other novel platforms will be pursued as resources and specimen availability permit.

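### Protocol 13.2.4.1 allows post-treatment marker levels to be tested as predictive by treatment-by-marker interaction, which can show an interaction where there is no effect modification

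*Protocol*

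**What the plan says.** Protocol 13.2.4.1 gives one method for every predictive analysis: "Analyses of the predictive ability of markers will be accomplished via standard tests of treatment-by-marker interaction". The test is to be fitted by logistic or Cox regression, depending on the outcome. Nothing confines the marker to a pre-dose value.

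Three items in Protocol 13.2.4 put post-treatment levels under that method, each against pathologic response and two-year RFS:

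- Item 4: "The prognostic and predictive relationship between pre- and post- treatment TIL and NK-cell level and activation".
- Item 7: "To assess the prognostic and predictive relationship of pre- and post-treatment T-cell subsets, CD4+/CD8+ and CD4+/FOXP3+ ratios and plasma cytokine multiplex panels".
- Item 8: "To assess the prognostic and predictive relationship between pre- and post-neoadjuvant treatment levels in plasma cytokine biomarkers of interest".

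Protocol 2.3 carries the same objectives. For IHC it asks "To assess the prognostic and predictive value of the expression of baseline immunohistochemistry (IHC) markers of interest", continuing "and change in expression, for pathologic partial and complete tumor response"; the PBMC subset objective is worded in the same way.

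The protocol also treats these markers as responding to the drugs. Section 14.2.5 says "The pharmacodynamics functional effects of nivolumab and/or lirilumab will be analyzed by assessment of pre- and post-treatment plasma cytokine markers of interest". Section 13.2.2.1 hypothesises a TIL density change of about 3.0 per 100 tumor cells and gives 82% power for a 0.80 SD cohort difference at cystectomy.

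The only caveat, at the end of 13.2.4.1, is that the study is not powered for these analyses and that conclusions on predictive ability will be limited.

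The SAP keeps the post-treatment predictive objectives (3.3, 7.4.3.2, 7.4.3.5, 7.4.3.6). It lists the IHC and PBMC objectives, including change, as secondary (3.2). It contains no treatment-by-marker interaction test, and 7.4.3 gives no method for items 7.4.3.2, 7.4.3.5 and 7.4.3.6. SAP 2.1 says the SAP supersedes the protocol's statistical considerations, and SAP 8 declares no changes.

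**The concern.** A treatment-by-marker interaction shows that a marker is predictive only if the marker is fixed before treatment. A post-treatment level is partly an outcome. Its interaction with cohort mixes three things: how the drugs move the marker, how response moves the marker, and any real effect modification. Cystectomy TIL density is the clearest case, because it is read from the same specimen whose pathology defines response (Protocol 10.4 and 14.1.2).

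At stake is a marker being reported as predictive when the data show only that the drug effect on it was more variable in one cohort, or that response changed it more in one cohort. This is bias: a larger follow-on study would find it more often. Protocol 1.8 presents the trial as a platform for biomarker discovery and validation that will inform development, so the label may carry weight later.

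**Working it through.** **1. The plan's nearest figure.** The documents give no figure for the interaction tests. The 82% power for 0.80 SD (12 against 24, one-sided 0.10) is the closest, since it shows that the design looks for a cohort difference in a post-treatment marker. The noncentrality is 0.80 × √(12 × 24 / 36) = 2.26. The normal approximation gives Φ(2.26 − 1.28) = 83.7%, noncentral t gives 83.0%, the Wilcoxon efficiency factor 3/π brings it to 81.6%, and a simulated rank sum test gives 81.8%. The figure reproduces.

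**2. Case (a): the marker change is more variable in one cohort.** Let B be a baseline marker, N(0,1), with the same odds ratio (OR) for response in both cohorts, so there is no effect modification. The post-treatment marker is M = B + 0.8T + noise, where T marks Cohort 2 and the noise SD is s. The slope on M in a cohort is then approximately log(OR) / (1 + s²). The 0.8 shift does not enter this slope. Take s = 0.5 in Cohort 1, so the factor is 1/1.25 = 0.80. In Cohort 2 the factor is 1/2 = 0.50 for s = 1.0 and 1/3.25 = 0.308 for s = 1.5.

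| OR per SD | Cohort 2 s | Slope, Cohort 1 | Slope, Cohort 2 | Ratio of ORs, formula | Simulated (400,000 patients) |
|---|---|---|---|---|---|
| 3 | 1.0 | 0.879 | 0.549 | exp(−0.330) = 0.72 | 0.70 |
| 3 | 1.5 | 0.879 | 0.338 | exp(−0.541) = 0.58 | 0.57 to 0.58 |
| 1.5 | 1.0 | 0.324 | 0.203 | exp(−0.122) = 0.89 | 0.88 to 0.89 |
| 1.5 | 1.5 | 0.324 | 0.125 | exp(−0.200) = 0.82 | 0.81 to 0.82 |

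With equal spread the simulated ratio is 0.98 to 0.99. With the baseline marker it is 1.00.

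**3. Case (b): response raises the marker.** Let M be N(0,1) plus d in responders, with d depending on cohort. The log OR per SD within a cohort then equals d. With d = 0.8 in Cohort 2 and 0.4 or 0 in Cohort 1, the ratio is exp(0.4) = 1.49 or exp(0.8) = 2.23 (simulated 1.5 and 2.2). An equal rise in both cohorts gives 0.99.

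**4. A second simulation set.** Response is about 30% in both cohorts in the first two rows, and no baseline effect modification is built in. Rejection is by likelihood-ratio test at two-sided 0.05, shown as post-treatment marker against baseline marker.

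| Drug effect on the marker | Interaction log OR, post vs baseline | Rejection, 12+24 | Rejection, 120+240 |
|---|---|---|---|
| Rises 0.8 SD in Cohort 2 responders only | 0.79 vs about 0 | 20% vs 9% | 89% vs 6% |
| Variable rise in Cohort 2 (mean 0.8, SD 1.0); baseline marker prognostic | −0.44 vs about 0 | 14% vs 11% | 42% vs 4% |
| Uniform 0.8 SD shift, logit-linear | about 0 vs about 0 | 11% vs 11% | 3% vs 3% |

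At 12+24, the more extreme settings of steps 2 and 3 give 15% against 10% in (a) and 20% against 9% in (b). The milder ones give 11% against 11% and 12% against 9%. Wald tests reject at most 9% of the time.

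**5. What is assumed.** The ORs, spreads, response rates and response-driven rises are assumptions; the documents give none of them. The protocol's 0.80 SD does not anchor case (b). With response rates of 25% and 35%, the implied cohort difference there is only 0.35 × 0.8 − 0.25 × 0.4 = 0.18 SD, or 0.35 × 0.8 = 0.28 SD.

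**The case against.** The strongest reply is that little depends on these tests. The protocol calls them exploratory and already says that conclusions will be limited. With 12 and 24 patients the likelihood-ratio test rejects 9% to 11% of the time even on baseline markers with no interaction, so small-sample unreliability matters about as much as the bias in most settings. This stands as a limit on weight. It does not remove the point, because the caveat concerns power.

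A reader might go further than the documents allow in four ways:

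- **That a marker which merely records receipt of lirilumab would look predictive.** A uniform shift, or equal spread in both cohorts, gives a ratio of about 1.0. Unequal variability or an unequal response-driven rise is needed, and the documents give no spread of change by cohort.
- **That on-treatment changes will be interaction-tested.** Section 13.2.4.1 gives changes a rank sum comparison, and items 1 and 2 of 13.2.4 speak only of a relationship. The link runs only through the wording of Protocol 2.3, so it is weaker than for levels.
- **That a marker will be used to select patients for lirilumab.** Neither document says so.
- **That the SAP prescribes the test.** It does not. Its marker methods are t-tests or rank sum tests, Fisher's exact test and survival comparisons (7.4.2.6, 7.4.2.7, 7.7.6, 7.7.7). The nearest thing is a comparison of cohort and response stratified by IHC level in 7.4.2.6. Because SAP 8 declares no changes, whether the protocol's test still applies is unresolved.

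**Conclusion.** The concern holds for post-treatment levels in items 4, 7 and 8 of Protocol 13.2.4. As written, 13.2.4.1 allows a test that cannot identify effect modification for markers the protocol expects the drugs to alter. With no true effect modification, the ratio of odds ratios is 0.88 to 0.58 for unequal spread (OR 1.5 to 3 per SD; Cohort 2 spread 1.0 to 1.5 SD against 0.5 SD). It is 1.5 to 2.2 for an unequal response-driven rise, against 1.0 with the baseline marker. These sizes rest on the assumed inputs above. The bias is possible, not certain, and modest in its effect on rejection rates at this sample size. The primary and key secondary analyses are not affected. The wording should be corrected before the marker analyses are run.

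**What to change.** - In Protocol 13.2.4.1, restrict treatment-by-marker interaction tests, and the word predictive, to markers measured before the first dose.
- Report post-treatment levels as pharmacodynamic effects by cohort, and as within-cohort associations with response and RFS.
- Amend items 4, 7 and 8 of Protocol 13.2.4 and the matching objectives in Protocol 2.3, including the predictive value of change in IHC and PBMC markers. Amend SAP 3.2, 3.3, 7.4.3.2, 7.4.3.5 and 7.4.3.6 to match.
- Reconcile the SAP with the protocol: either carry the restricted interaction test into the SAP, or list its omission as a change in SAP 8.
- State that even a baseline-marker interaction compares sequential, non-randomised cohorts, so it is confounded with enrolment period and is hypothesis-generating only.

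The cost is wording in two documents. No samples or data are lost and fewer tests are run. The one thing given up is any predictive claim for a post-treatment marker.

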10.2 CD8+ T-Cell Density

The CD8+ T-cell density is defined as the number of CD8+ tumor-infiltrating T-cells per 100 tumor cells within a 400x high power field (HPF). The CD8+ T-cell density will be calculated as:

Tumor Infiltrating CD8+ T-cell density (CD8+ T-cells per 100 tumor cells) =
(Total # of CD8+ TILS)/ (Total # of tumor cells per HPF) x 100

Five representative tumor fields with the greatest gross tumor infiltrating lymphocyte fields (minimum 100 tumor cells per representative field) will be chosen for measurement by microscope analysis by the pathologist with the final CD8+ T-cell density determined as the mean of the CD8+ T-cell density across the five fields.

10.3 %CD8+ Tumor-Infiltrating T-Cells

The %CD8+ tumor-infiltrating T-cells will be quantified by immunohistochemistry (IHC) analysis of tissue. Using semi-automated image analysis, a staining percentage determined by dividing the area of brown 3,3'-Diaminobenzidine (DAB) staining by the area of epithelial cells will be obtained.

Five representative tumor fields with the greatest gross tumor infiltrating lymphocyte fields will be chosen for measurement by the pathologist with the final %CD8+ tumor-infiltrating T-cells determined as the mean of the %CD8+ tumor-infiltrating T-cells across the five fields.

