14.1.2 Tumor Infiltrating CD8+ T-Cell Density

Post-treatment tumor infiltrating CD8+ T-cell density is the secondary endpoint of the trial. In pre- and post-treatment tumor tissue specimens CD8+ T-cell density will be examined by IHC performed on whole tissue histology sections. The CD8+ T-cell density is defined as the number of CD8+ tumor-infiltrating T-cells per 100 tumor cells within a 400x HPF.^{12,45} Five representative tumor fields with the greatest gross tumor infiltrating lymphocyte fields (minimum 100 tumor cells per representative field) will be chosen for measurement by microscope analysis by the pathologist with the final CD8+ T-cell density determined as the mean of the CD8+ T-cell density across the five fields. CD8 IHC on both the pre- and post-treatment will be performed by a central pathology lab. Pre- and post-treatment CD8+ staining cells intermixed within surrounding tumor cells will be considered tumor infiltrating CD8+ T-cells. These cells will be counted as will the number of tumor cells within the chosen 400x HPF. The CD8+ T-cell density will be calculated as:

Tumor Infiltrating CD8+ T-cell density (CD8+ T-cells per 100 tumor cells) =

(Total # of CD8+ TILS)/ (Total # of tumor cells per HPF) x 100

In addition, CD8+ TIL density will be assessed by central pathology review using image analysis of five 1-mm-sq areas using image analysis (Aperio, Leica Biosystem). Additionally, eight areas of highest inflammatory infiltrate (“hot-spots”) will be reviewed by image analysis to document focal or diffuse process of inflammation. This methodology will be utilized to determine both the pre- and post-treatment tumor infiltrating CD8+ T-cell densities.

For additional analysis, tissue microarrays (TMAs) of pre- and post-treatment tumor tissue biopsies will be constructed using available tumor FFPE blocks. The TMAs will be constructed using three 1.0 mm diameter tumor core tissues containing at least 100 malignant cells. Also, a minimum of 20 (30 preferred) unstained 5 micron thick sections from both the pre- and post-treatment tumor samples will be cut into slides for additional correlative investigations. In the event that a patient’s post-treatment TMA section is not suitable for averaging three representative tumor infiltrating lymphocyte regions, the post-treatment slides may be used for the CD8+ T-cell density analyses.

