14.1.3 Percentage CD8+ Tumor Infiltrating T-Cell

Utilizing tissue slides described above in Section 14.1.2, the %CD8+ tumor infiltrating cells pre- and post-treatment will be quantified by semi-automated image analysis. CD8+ tumor infiltrating IHC percentage will be determined by dividing the area of brown 3,3'-Diaminobenzidine (DAB) staining by the area of epithelial cells within HPF. The final %CD8+ tumor infiltrating T-cell measurement will be determined by an average of five representative tumor fields with the greatest gross tumor infiltrating lymphocytes.

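### The signed-rank test planned for comparing CD8+ density methods measures shift, not relationship, and cannot be interpreted unless the methods share a scale that the protocol never states

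*Protocol*

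**What the plan says.** Protocol 13.2.4.1 gives one sentence on comparing methods. It pairs Pearson's correlation with a second tool: "the Wilcoxon signed rank test will be used to characterize the relationship between CD8+ TIL densities produced by various methods of assessment". It does not list the methods or say whether the comparison is by cohort or pooled, or by time point. The same section says that the study is not powered for the exploratory analyses.

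The CD8+ measurements are described elsewhere:

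- **Manual microscopy (Protocol 10.2, 14.1.2).** The density is "the number of CD8+ tumor-infiltrating T-cells per 100 tumor cells within a 400x high power field", averaged over five fields chosen for the most lymphocytes.
- **Image analysis (Protocol 14.1.2).** The density is also "assessed by central pathology review using image analysis of five 1-mm-sq areas". No denominator or unit is given, and no rule for choosing the areas.
- **Hot-spots (Protocol 14.1.2).** Image analysis also reviews "eight areas of highest inflammatory infiltrate", to show whether inflammation is focal or diffuse. Neither size nor unit is stated.
- **%CD8+ (Protocol 10.3, 14.1.3).** This divides the area of brown DAB "staining by the area of epithelial cells within HPF". It is called a percentage, not a density.

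The SAP lists the image-analysis objective at 7.4.3.9 without any between-method analysis. SAP 2.1 says that the SAP supersedes the protocol's statistics, and SAP section 8 says that no changes are planned.

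**The concern.** The stated aim is to characterize a relationship. A paired test of zero difference does not do that on any scale: two methods can rank patients identically and differ by a constant factor, or be unrelated and have the same centre. The test answers a question about shift, and the shift has meaning only if both methods report in the same unit.

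The documents do not settle whether they do. Even with one unit the regions differ, because the manual fields are selected for lymphocytes and the rule for the 1-mm-square areas is not given. A shift could then come from field selection rather than from the method of counting.

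Pearson's coefficient fits the aim better but is limited to linear association. It would be the same if one method read systematically higher than the other by a fixed factor. In small samples a few large values can determine it.

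At stake is the readability of the only planned comparison across CD8+ methods, in a trial whose key secondary endpoint is a CD8+ density. A significant p value could be read as poor agreement, or a non-significant one as good agreement, and neither would follow.

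**Working it through.** **Is there a planned figure to reproduce?** No. The documents give no sample size, power or significance level for this comparison.

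**Inputs from the documents.** SD of the manual density 3.9 per 100 tumor cells (Protocol 13.2.2.1). Patients: 12 in Cohort 1 and 24 in Cohort 2, 36 in total (same section).

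**Assumptions.** Manual density X is lognormal with SD 3.9 and mean 3, 6 or 10. Second method Y is k times a lognormal variable with the same mean and SD, correlated ρ with X on the log scale. The factor k stands for a scale difference between methods. Tests are two-sided at 0.05, n is 12, 24 or 36, with 800 runs per setting.

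**Step 1: a pure scale difference.** If Y = kX with k > 1, every difference (k − 1)X is positive, so the signed-rank statistic is at its extreme. The exact two-sided p is then 2/2^n:

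- n = 12: 2/4,096 = 0.00049
- n = 24: 2/16,777,216 = 1.2 × 10^-7

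Pearson and Spearman both equal 1 here. These p values assume complete pairs analysed by cohort, which the plan does not specify.

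**Step 2: simulation.** Ranges are over the three means and three sample sizes.

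| Setting | Signed-rank rejects | Mean Pearson r | Mean concordance coefficient |
|---|---|---|---|
| Same scale, unrelated (k=1, ρ=0) | 3.7–5.5% | about 0 | about 0 |
| Same scale, closely related (k=1, ρ=0.95) | 3.4–6.1% | 0.93–0.94 | 0.89–0.94 |
| 20% proportional shift (k=1.2, ρ=1) | 100% | 1.00 | 0.86–0.97 |
| Tenfold scale, unrelated (k=10, ρ=0) | 99.6–100% | about 0 | about 0 |
| Tenfold scale, perfectly related (k=10, ρ=1) | 100% | 1.00 | 0.03–0.12 |
| Fiftyfold scale, unrelated (k=50, ρ=0) | 100% | about 0 | about 0 |
| Fiftyfold scale, perfectly related (k=50, ρ=1) | 100% | 1.00 | 0.005–0.02 |

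The Monte Carlo standard error near 5% is √(0.05 × 0.95/800) = 0.0077, so the first two rows do not differ in rejection rate.

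**Step 3: hand check of the concordance coefficient.** For Y = kX it is 2k·s² / [(1 + k²)s² + (k − 1)²m²]. With s = 3.9 (s² = 15.21), m = 6 and k = 1.2: 36.504 / (37.1124 + 1.44) = 0.947. With k = 10: 304.2 / (1,536.21 + 2,916) = 0.068. Both are slightly above the simulated means at m = 6 (0.932–0.941 and 0.058–0.065), which are averages of small-sample estimates.

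**Reading the results.**

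- On one scale, non-rejection does not distinguish unrelated from closely related methods.
- On one scale, the test does detect a 20% shift.
- Across scales, rejection is near certain whatever the relationship.
- Pearson's r is 1.00 at a 1.2-, 10- or 50-fold difference, so it cannot show agreement.
- The concordance coefficient also collapses under a scale difference, so it too belongs only on a common scale.

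The sensitivity of Pearson's r to a few high values is a general property of the coefficient. It was not simulated separately.

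**The case against.** The best defence is that the documents never say the units differ. The only unit given for CD8+ TIL density is per 100 tumor cells. Protocol 14.1.2 states that formula and then uses the same term for image analysis, so the 1-mm-square areas may be just the sampling region, as the 400x field is for microscopy. %CD8+ has a plainly different unit but is named separately and may fall outside a sentence about densities. On a common scale a signed-rank test for systematic shift is legitimate, and shift is one component of agreement. The plan says relationship, not agreement. Pearson is unit-free and does describe linear relationship.

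Most of this stands. A reader might infer that the test is bound to reject because of units, whatever the agreement. The documents do not support that: a per-mm-square unit is plausible but not stated, and on one scale without shift the simulated rejection rate is near 5%. A reader might also infer that image analysis is meant to replace the manual count. No section says so. Nor is there a case for removing the test outright, since it has a proper use on a shared scale.

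The defence does not rescue the test for its stated purpose. Even with one unit it measures shift, not relationship, and the reader cannot tell whether the unit is shared.

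**Conclusion.** The point holds in a limited and partly conditional form. Unconditionally, the signed-rank test does not characterize a relationship, and Pearson's coefficient does not measure agreement. Conditionally, if the image-analysis density is not per 100 tumor cells, the signed-rank result reflects scale alone and is uninterpretable.

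The simulated rates rest on assumed lognormal distributions, means, scale factors and a 0.05 level. They illustrate how the tests behave and do not predict this trial's results. The conclusion about what each statistic measures does not depend on them.

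The consequence is small. The analysis is exploratory and declared unpowered, and the key secondary endpoint uses the manual definition. The label is cheap improvement.

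**What to change.** Revise the sentence in Protocol 13.2.4.1 and enter the same text as the analysis under SAP 7.4.3.9, which now has none:

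1. List the CD8+ methods being compared, and state the unit, denominator and field-selection rule of each.
2. Across all methods, report Spearman correlation (with Pearson alongside if wanted) for the density and for the TURBT-to-cystectomy change.
3. For methods on the same scale, add Bland-Altman bias and limits of agreement, or a concordance coefficient.
4. Restrict the signed-rank test to methods on the same scale, and describe it as a test of systematic shift only.

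The cost is a short text change in each document and slightly more exploratory output. The one loss is that there is no between-method p value where units differ.
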